7.2 OBJECTIVES

To evaluate whether prescribers and the patients/carers have understood the requirements of and report adherence with the additional RMMs associated with Hemlibra®. The objectives of the study are as follows:

Prescriber (HCP) survey

- Assess prescriber awareness of the Hemlibra® educational program by estimating the proportion of targeted prescribers who acknowledge having received and read the relevant educational materials.
- Assess prescriber knowledge of:
 - the important identified risks of TMA and TEs that may occur if a cumulative amount of >100U/kg/24 hours for 24 hours or more of aPCC is used concomitantly with Hemlibra® and
 - the important potential risk of life-threatening bleeding due to misinterpretation of the standard coagulation tests, which may be unreliable in patients treated with Hemlibra®,by estimating the proportion of targeted prescribers with correct responses to risk knowledge questions.
- Assess self-reported prescriber adherence to the additional RMMs, by estimating the proportion of targeted prescribers whose responses to the practice-related questions are consistent with the Guide for Healthcare Professionals.

Patient/carer survey

- Assess patient/carer awareness of the Hemlibra® educational program by estimating the proportion of patients who acknowledge having received and read the Patient/Carer Guide and Patient Alert Card.
- Assess patient/carer knowledge of:
 - the important identified risks of TMA and TEs that may occur if a cumulative amount of >100U/kg/24 hours for 24 hours or more of aPCC is used concomitantly with Hemlibra® and
 - the important potential risk of life-threatening bleeding due to misinterpretation of the standard coagulation tests, which may be unreliable in patients treated with Hemlibra®,by estimating the proportion of patients/carers with correct responses to risk knowledge questions.
- Assess patient/carer self-reported adherence to the additional RMMs, which will be evaluated by estimating the proportion of patients/carers whose responses to the questions are consistent with the Patient/Carer Guide and Patient Alert Card.

The objectives for the survey will be aligned with any key elements to be addressed in these studies provided by the Pharmacovigilance Risk Assessment Committee (PRAC).

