8.3 VARIABLES

The following variables are collected:

Prescriber (HCP) survey

- Variables related to HCP participation
 - Response rate
 - Refusal rate
- Variables related to HCP practice information:
 - Location (city/country)
 - HCP primary specialization
 - Years practicing as a physician
 - Practice setting (Haemophilia Comprehensive Care Centre, haemophilia treatment centre, hospital haematology department, other)
 - Past experience with Hemlibra® (overall number of patients, number of patients with inhibitors, and severe patients without inhibitors treated)
 - Participation as a Hemlibra® clinical trial investigator
 - Last time prescribing Hemlibra®
 - Makeup of patient population (adults or children)
- Variables related to HCPs' awareness of the Hemlibra® educational program
 - Receipt of each of the RM tools (Patient Alert Card, Patient/Carer Guide, Guide for Healthcare Professionals) (yes/no)
 - Reading of the Guide for Healthcare Professionals (yes/no)
- Variables related to the HCPs' knowledge of the risks associated with the use of Hemlibra®, as described in the educational materials:
 - Knowledge of guidelines on the use of bypassing agents in their patients receiving Hemlibra® prophylaxis, particularly for TMA and TE with concomitant aPCC use (true/false statements)
 - Knowledge of laboratory coagulation tests which have their reliability affected by Hemlibra® and associated recommendations (tick boxes with answers that are either consistent or inconsistent with the additional RMMs)
 - Knowledge of time period to follow dosing and laboratory testing guidelines (tick boxes with answers that are either consistent or inconsistent with the additional RMMs)
- Variables related to the HCPs' self-reported adherence to the educational measures by correct implementation of the additional RMMs:
 - Distribution of Patient Alert Cards and Patient/Carer Guides to patients receiving Hemlibra® prophylaxis (or their carers) (tick boxes listing frequency of distribution of RM tools to patients)

- Counselling of patients or their carers to carry the Patient Alert Card for 6 months after their last dose of Hemlibra (tick boxes with answers that are either consistent or inconsistent with the additional RMMs)
- Use of aPTT test results in patient who receive Hemlibra® (yes/no)
- Precautions followed when prescribing Hemlibra® (tick boxes with answers that are either consistent or inconsistent with the additional RMMs)

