- Bypassing dosing guidance in their patients receiving Hemlibra® prophylaxis (tick boxes with answers that are either consistent or inconsistent with the additional RMMs)

Patient/carer survey

- Variables related to the patients treated with Hemlibra®:
 - Completion by patient or carer
 - Patient age (years)
 - Time since last dose of Hemlibra® (tick boxes with ranges of treatment duration in months)
 - Diagnosis with FVIII inhibitors (yes/no)
 - Severity of disease (mild/moderate/severe)
 - Receiving at least 4 doses of Hemlibra® in the last 6 months (yes/no)
- Variables related to the patients' awareness of the Hemlibra® educational program, or the awareness of their carer if the patient is under the age of 18:
 - Receipt of Patient Alert Card and Patient/Carer Guide (tick boxes for receipt)
 - Discussion with HCPs of risks associated with the use of Hemlibra® (yes/no)
 - Reading of the received educational materials (yes/no)
- Variables related to the patients' knowledge about the risks of Hemlibra®, or the knowledge of their carer if the patient is under the age of 18:
 - Knowledge of risks associated with the use of Hemlibra® (tick boxes with answers that are either consistent or inconsistent with the additional RMMs)
 - Knowledge that the Patient Alert Card should be carried at all times (tick boxes with answers that are either consistent or inconsistent with the additional RMMs)
 - Knowledge that Hemlibra® use can affect laboratory tests on blood clotting (true/false)
 - Knowledge of aPCC dosing and risks of concomitant use with Hemlibra® therapy (true/false statements)
- Variables related to the patients' self-reported adherence to the educational measures by correct implementation of the additional RMMs, or the self-reported adherence of their carer if the patient is under the age of 18:
 - Showing the Patient Alert Card to health care professionals (yes/no)
 - For patients taking aPCC while taking Hemlibra®:
 - Taking a first dose of aPCC of <50U/kg
 - Contacting their HCP before increasing the dose of aPCC above 50U/kg (yes/no/not applicable)
 - Not taking >100U/kg/24 hours for 24 hours or more (yes/no)

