8.7.4 Questionnaire Analysis

Analysable questionnaires are those completed and submitted by the participants on the web. If the questionnaire is just filled on the web but not submitted, the questionnaire will not be analysed and will be discarded.

Analysis will be done on questions common to all HCPs and patients/carers as well as on a limited number of questions presented to the subgroup of patients with concomitant use of aPCC and Hemlibra® (or their carers).

For each question, the number and percentage of participants correctly answering each question will be presented. Individual awareness, knowledge, and adherence values will be calculated as the percentage of correctly answered questions; values will range from 0 to 100% with 100% representing the percentage of all questions in the category being answered correctly.

Awareness questions

- HCP questionnaire: Q8 and Q9
- Patient/carer questionnaire: Q1 and Q2

Knowledge questions

- HCP questionnaire: Q10, Q11, and Q12
- Patient/carer questionnaire
 - All: Q3, Q4, Q5, and Q6

Adherence questions

- HCP questionnaire: Q13, Q14, Q15, Q16, and Q17
- Patient/carer questionnaire
 - All: Q11
 - Additional questions for patients (or their carers) taking aPCC and Hemlibra: Q8, Q9, and Q10

In a first step, calculations will be performed on raw data. No projection factor will be applied to generalize the results to the entire prescribers' universe. As a consequence, the line "Overall - unweighted results" will show only the results observed on the overall sample and will not reflect the geographies' universe since this sample is not proportional to the size of the lists in each geography.

If possible, in a second step, the results will be weighted according to the real proportion of HCPs or patients/carers in a geographical region in order to accurately reflect the population that the survey seeks to measure.

Possible *participation* bias will be assessed by comparing the distributions of available characteristics (e.g., geography, type of setting [e.g., haemophilia treatment centre or HCCC], and speciality, if applicable and feasible) between respondents and non-respondents.

Assessment of success

The proportions of correct and appropriate answers to selected questions asked in the questionnaire will be presented for HCPs or patients/carers who provided answers to those questions, as outlined below.

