Successful outcomes for the effectiveness of risk minimisation measures in the aspects of awareness, knowledge, and adherence are defined a priori by the following target levels:

For HCPs

- Awareness: Proportion of HCPs aware of the Hemlibra® educational program (Q8 and Q9) – Success: $\geq 75\%$
- Knowledge: Proportion of HCPs with knowledge of the important identified risks and potential risks associated with Hemlibra treatment (Q10, Q11, and Q12) – Success $\geq 60\%$
- Adherence: Proportion of HCPs self-reporting adherence to the additional RMMs for Hemlibra (Q13, Q14, Q15, Q16, and Q17) – Success $\geq 75\%$

For patients/carers

- Awareness: Proportion of patients/carers aware of the of the Hemlibra® educational program (Q1 and Q2) – Success: $\geq 60\%$
- Knowledge: Proportion of patients/carers with knowledge of the important identified risks and potential risks associated with Hemlibra treatment (Q3, Q4, Q5, and Q6) – Success: $\geq 60\%$
- Adherence: Proportion of patients/carers self-reporting adherence to the additional RMMs for Hemlibra (Q11) – Success: $\geq 60\%$

- Proportion of patients taking aPCC and Hemlibra (or their carers) self-reporting adherence to the additional RMMs specific for use of aPCC and Hemlibra (Q8, Q9, and Q10) - Success: $\geq 60\%$

Overall success is defined as success on all three domains measures (awareness, knowledge and adherence) for both HCPs and patients/carers.

Exploratory analysis of HCPs with higher success rates will also be performed and the percentage of HCPs who answered 80% and 90% of the questions correctly in each of domain will be calculated.

A sensitivity analysis will be performed to assess and compare the results of HCPs who were investigators in Hemlibra clinical studies (i.e., HAVEN) with the ones from HCPs who have prescribed Hemlibra exclusively in routine clinical practice.

Profile of HCPs with incorrect answers

The profile of HCPs with incorrect answers to the questions related to the three success factors will be described using all available and relevant HCPs characteristics collected in the survey (e.g., geography, speciality, duration of practice, practice setting) and past experience with Hemlibra® (number of patients prescribed).

Profile of patients with incorrect answers

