The profile of patients with incorrect answers to the questions related to the three success factors will be described using all available and relevant patient characteristics collected in the survey (e.g. geography, age, diagnosis with inhibitors).

Note that other additional analyses will be performed. These include the comparison of the knowledge and adherence to additional RMMs of HCPs and patients that are aware of the additional RMMs as opposed to those who are not aware of the RMMs.

Analyses will be defined in more detail in the SAP and final report.

Note that the selection of these thresholds for success is subjective (7 May 2015 PRAC Rapporteur PASS Protocol Assessment Report; Procedure no.: EMEA/H/C/000387/MEA 087.2) and not based on a priori knowledge, experience, or established scientific criteria in the education or risk communication or evaluation literature. Therefore, the results will be contextualized considering other available information.

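### The aware-versus-unaware adherence comparison is partly built in for patients/carers, because awareness includes receiving the Patient Alert Card and the only all-patient adherence item appears to be showing it

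*Protocol*

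**What the plan says.** **The comparison.** Among the additional analyses, section 8.7.4 commits to a "comparison of the knowledge and adherence to additional RMMs of HCPs and patients that are aware of the additional RMMs" against those who are not. No item is excepted and the comparison is not limited to recipients. Section 8.9 (limitations) does not mention a dependence between the two sides.

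**The grouping variable.** For patients/carers, section 7.2 defines awareness by "estimating the proportion of patients who acknowledge having received and read the Patient/Carer Guide and Patient Alert Card". Section 8.3 lists "Receipt of Patient Alert Card and Patient/Carer Guide (tick boxes for receipt") among the awareness variables, with reading of the materials and a risk discussion with the HCP. For HCPs, the awareness variables include "Receipt of each of the RM tools (Patient Alert Card, Patient/Carer Guide, Guide for Healthcare Professionals) (yes/no") and reading of the HCP guide.

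**The outcome.** Section 8.7.4 defines the patient target as "Adherence: Proportion of patients/carers self-reporting adherence to the additional RMMs for Hemlibra (Q11"). It adds a separate set, "Additional questions for patients (or their carers) taking aPCC and Hemlibra: Q8, Q9, and Q10". In section 8.3 the only patient adherence variable not restricted to aPCC users is "Showing the Patient Alert Card to health care professionals (yes/no"). HCP adherence has five questions (Q13 to Q17) and five listed variables, the first being "Distribution of Patient Alert Cards and Patient/Carer Guides to patients receiving Hemlibra® prophylaxis (or their carers").

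**The concern.** A patient who never received the card cannot show it. That patient is unaware by the section 7.2 definition and, if asked Q11, non-adherent by necessity. Receipt then enters both sides of the patient comparison, and a difference appears whether or not the materials influence anyone's behaviour.

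The study exists to assess whether the risk minimisation measures are effective, and this is the one analysis in the protocol that sets contact with the materials against behaviour. A large gap invites the reading that the materials work, when part of it, possibly all, only records who was given a card.

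**Working it through.** **The plan's own figures.** The protocol gives no figure for this comparison. Its only statistical figures, in Table 2 of section 8.5.1, reproduce. With n = 0.25 × 1.96² / e², half-widths of 15%, 12%, 11% and 10% give 42.7, 66.7, 79.4 and 96.0, against the stated 43, 67, 80 and 96. They are not at issue.

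**Which question is Q11?** The questionnaires are not shown. Section 8.3 lists four patient adherence variables: showing the card, and three for aPCC users. Section 8.7.4 gives Q11 to all patients and three questions (Q8 to Q10) to aPCC users. By elimination Q11 is showing the card.

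**Patients, if non-recipients answer Q11.** Suppose reading the materials changes nothing. Let s be the share of cardholders who show the card, the same in both groups, and q the share of the unaware group without a card.

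- Aware group (all hold a card under section 7.2): s
- Unaware group: q × 0 + (1 − q) × s = s(1 − q)
- Built-in gap: s − s(1 − q) = s × q

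The protocol gives neither s nor q, so both are assumptions:

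| s | q = 0 | q = 0.25 | q = 0.50 | q = 1 |
|---|---|---|---|---|
| 60% | 0 | 15 | 30 | 60 |
| 90% | 0 | 22.5 | 45 | 90 |

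(gap in percentage points)

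For scale, take the target of 70 patients, 60% to 75% of them aware, and s = 60%. A Fisher test would fall below 0.05 in about 51% to 63% of simulated surveys at q = 0.5, against 3% to 4% at q = 0. No test is planned; this only shows that the artefact can stand out from sampling noise.

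**Patients, if non-recipients skip Q11.** Section 8.7.1 removes missing answers from the denominator. The unaware group then contains only people who hold a card but did not read the materials or lack another tool. The built-in gap disappears, but the result no longer compares all aware with all unaware patients.

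**HCPs.** Section 8.7.4 scores adherence as the percentage of the five items answered correctly. This assumes one question per listed variable. Let p be the correct rate per item, equal in both groups for HCPs who hold the tools, k the number of items that need the tools, and q the share of unaware HCPs who never received them. The gap is k × p × q / 5.

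- k = 1 (distribution), p = 75%: 1 × 0.75 × 1 / 5 = 15 points at q = 1; 7.5 points at q = 0.5
- k = 2 (adding counselling to carry the card), p = 75%: 30 points at q = 1; 15 points at q = 0.5
- Ceiling at p = 100%, q = 1: 20 points (k = 1) or 40 points (k = 2)

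**After restriction.** Among recipients only (q = 0), or with tool-dependent items removed (k = 0), the built-in gap is zero in both surveys.

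**The case against.** **Detail is left to the SAP.** The protocol gives this analysis one sentence and defers the rest, and the SAP could restrict it to recipients without contradiction. That is fair as to detail. But the protocol itself fixes the contrast, the receipt-based definition of awareness and the single all-patient item, and the problem follows from those three.

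**Routing cannot be seen.** Section 8.6.1 mentions skip patterns, so non-recipients may never be asked Q11. This stands as an uncertainty. The visible text leans the other way: Q11 is listed for all patients, section 8.7.5 requires an answer before proceeding, and section 8.3 gives a not-applicable option for one aPCC variable but only yes or no for the card.

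**The unaware may hold cards.** They can include people who received the card without reading it, or who lack only the guide. This stands, and it is why the gap scales with q.

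**Supplying the card is part of the measure.** Lower card use among people not reached is a genuine failure of implementation. This also stands, but it is a finding about supply, which receipt already measures, and should be reported as such.

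**Stronger readings.** A reader might infer that the HCP comparison is circular too. It is not: only distribution clearly needs the tools, counselling arguably does, and three items do not. A reader might also infer that the study's conclusion on effectiveness is compromised. The comparison is descriptive, enters none of the success thresholds in section 8.7.4, and is nowhere called an effect in the protocol.

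**Conclusion.** The point holds in a limited form. For patients/carers the comparison on Q11 is partly built in: with no influence of reading, the gap is s × q, or 15 to 30 points at an assumed s of 60% and q of 25% to 50%, and nil if every unaware patient holds a card. This rests on Q11 being the card item (inferred by elimination) and on non-recipients answering it. If they are skipped, the gap goes but the contrast changes meaning, so the plan needs a statement either way. For HCPs the five-item score is contaminated by one item clearly and a second arguably.

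The knowledge comparison, Q8 to Q10 in aPCC users, the success criteria and the sample size are untouched. The consequence is for interpretation, and it is worth correcting because the correction is cheap.

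**What to change.** In section 8.7.4, and in the SAP to match:

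1. Report Q11 and the HCP distribution item by awareness only among respondents who received the relevant tool, comparing those who read the materials with those who did not. For HCPs, section 8.3 records reading only for the HCP guide, so that is the split available.
2. Show the share who never received each tool separately, as a supply failure.
3. Base the full aware-versus-unaware adherence contrast on items that do not need the tool: the remaining four HCP items (three if counselling to carry the card is also set aside, a choice to state in advance), and Q8 to Q10 in aPCC users.
4. State whether non-recipients are asked Q11. If they are, note that they cannot answer yes.

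No new data are needed. The cost is that no all-patient adherence contrast remains beyond recipients, and the aPCC-user cells may be very small. Section 8.5.1 aims for 25 to 35 patients with inhibitors. Even if all of them took aPCC and, as assumed above, 25% to 40% were unaware, the unaware cell would hold about 6 (25 × 0.25) to 14 (35 × 0.40). Those results should be shown as counts and read with caution.

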8.7.5 Handling of Missing Data

The online questionnaires require responses before proceeding through the form, and missing data are expected to be few and distributed at random. Since there is no applicable method unanimously accepted, there will be no replacement or imputation of missing data ([Sterne et al. 2009](#)).

8.8 QUALITY CONTROL

8.8.1 Study Documentation

Data will be collected using a questionnaire administered online for both HCPs and patients/carers, and HCPs will also be given an option of a phone interview as an alternative.

Testing of questionnaire

For the online questionnaires, data will be collected using an electronic data capture (EDC) system developed following a full validation process. The programmed questionnaire will be tested and validated in accordance with IQVIA Standard Operating Procedures (SOPs), which cover validation for all clinical and risk management-related applications. The internet-based repository will be used to store survey data and other relevant program information. Questions are programmed to ensure that they are asked in the appropriate sequence. Skip patterns are clearly indicated. Respondents cannot go back to a question once the question has been answered and they cannot skip ahead. Response options presented in a list are randomized to minimise positional bias. Programming will be reviewed by Quality Control and simulated users (User Testing) prior to implementation.

Collected data will be entered and stored in a database specific to the survey and the country. A study database will be created by merging databases of each country. HCP identifying information will be stored separately from study data.

Data will be checked in terms of consistency before data analysis:

- Removal of duplicates (if required)
- Data labelling and data formatting
- Range and consistency checks for each variable to identify potential non-admissible values
- Cross-check the consistency of data for related variables (if feasible)

The study database will be locked once validated.

Approaches for language testing of the questionnaires

The HCP online questionnaire will be translated and tested in an initial release to two to three HCPs in several countries for its comprehensibility, consistency and the appropriateness of medical terms. HCPs comments will be implemented in the final version.

Similarly, the patient/carer online questionnaire will be tested with a sample of non-physicians, providing the educational materials for review before their completion of the questionnaire.

The translated versions of the questionnaire from English into local language will be done using the forward and *backward* method (from English into local language and then from local language into English) to ensure an accurate translation.

Approaches for validating the results

The quality control for validating the results will be conducted at five levels:

1. Every effort will be undertaken to collect complete and valid data
2. At the study database level, final data quality checks will be applied to count the number of missing values and estimate the associated relative percentage.
3. At the statistical analysis level: all data management and statistical analysis programs developed and used in the analysis will be documented. All versions generated will be dated, kept with accompanying documentation and archived. The original database will be stored. A derived database will be created for the new versions of the data in order to include recoding and computing of new variables, especially stratification of continuous variables, combination of modalities for categorical variables, calculation of composite indicators, etc.
4. At the results level, a data review will be done to ensure data integrity. A statistical analysis report including all the results will be provided for review and discussion. The final statistical report will take into account the reviewer's comments.
5. At the study level, all aspects of the study will be conducted according to the SOPs of IQVIA Real World Evidence Solutions. The study documents have been approved by people competent in medical and safety areas of IQVIA. According to the SOPs, an independent review of the study results and report will be conducted by a person who was not in charge of their preparation.

